6.5 Test Material and Administration

6.5.1 Islet Dosing and Administration

A minimum amount of islets of about 10,000 IE/kg recipient body weight is required for engraftment and confirmed C-peptide expression based on the Edmonton series. This form of procedure may require multiple transplants in order to reach this desired minimum number of islets, as previous clinical studies were unable to reliably reach insulin independence with a single transplant.

Eligibility for second or third islet infusion

Subjects are eligible for further transplant if by the end of the fourth week after the first islet infusion or by the end of the fourth week after the second islet infusion they do not meet insulin-independence criteria. If a subject does not reach the definition of insulin independence by the end of the third month after the third transplant, the subject may be considered for an exceptional fourth islet infusion. However, the indication for an exceptional fourth transplant needs to be presented to the Data Monitoring Committee and approval obtained.

Eligibility for islet retransplantation and/or fourth islet transplant:

Subjects are eligible for subsequent islet infusions if after a period of insulin independence of at least 30 days, they present with declining islet function requiring reintroduction of exogenous insulin. Subjects may receive this additional islet infusion anytime during the first year after the last islet infusion, or anytime during the 5-year follow-up, as long as no exclusion criteria are present and avoiding any HLAs (human leukocyte antigens) against which the recipient may have developed donor specific antibodies.

No maximum number of delivered islets is specified, except that the number must exceed 10,000 IE/kg following 2 islet transplants, and packed cell volume may not exceed 10 mL per transplant.

Transplant Procedure

Islets will be isolated from human pancreases procured from deceased multi-organ donors as described in Section 7. The islet isolation procedure will be performed in the clean room facilities of the Cell Isolation Laboratory at the University of Illinois at Chicago Hospital (see Section 7.4 *University of Illinois at Chicago Islet Processing Facility*). Isolated human pancreatic islets will be stored for a maximum of 12 hours before transplantation (see Section 7.2 *Product Manufacturing*).

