After the islet lot has been released by the PI, [name], or a co-investigator (see Section 7.6 *Product Testing*), and once the surgeon and subject are ready for infusion, the suspension is drawn directly into sterile 60 mL syringes. The 30 mL of transplant media containing the islets will be aspirated into the 60 mL syringe and the flask will be rinsed with 20 mL of transplant media. The 20 mL of transplant media will be aspirated in the 60 mL syringe. One 60 mL syringe will contain a maximum of 1 mL total packed islet cells. Alternatively to syringes, islets can be infused via a 600-mL iv bag-system.

The preparation will be labeled (see Section 7.3 *Product Label*), packed into sterile bags, and brought to the radiology suite via a hand carried insulating container at room temperature.

The radiology suite in which the procedure will be performed has access to emergency equipment, and the in-house anesthesiologist on call will be available to monitor the subject if necessary. Access to the surgical operation room is granted and a surgical team is available. The PI, [name], is a trained general and transplant surgeon with experience in the management of possible complications that could occur after islet transplantation such as bleeding from the puncture site or inability to access the portal vein by interventional radiology. In the absence of [name], a co-investigator will cover the service.

The subject will be admitted to the hospital as soon as an islet preparation is evaluated as potentially transplantable (sufficient islet mass and purity after purification). While release criteria of the islet cells are being evaluated, an eligible subject will be admitted and hospitalized in the Transplant Unit (7W UIC Hospital), and the immediate pre-transplant work-up will be performed as described in Section 6.6.4. The subject will remain in the Transplant Unit until the islet preparation is shown to fulfill the release criteria and is released for transplantation by the PI or a designee and the cross-match test is reported as negative. Then the subject will be brought to the radiology suite for transplantation. In the event that the islet preparation fails release criteria, the subject will be discharged from the hospital.

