If access to the portal vein cannot be gained by transvenous or transcutaneous approach, the subject will be brought to the operation theatre. A small laparotomy will be performed under local or general anesthesia, and portal access will be gained through cannulation of a mesenteric vein (24-26). The surgery will be performed by the PI, [name], or a co-investigator.

The islet preparation may consist of fractions of different purity with a total packed cell volume of less than 10 mL. If the total packed cell volume of the islet preparation is greater than 5 mL, the lot will be divided into two sub-lots during the purification process so that the higher purity fractions may be pooled separately from lower purity fractions and labeled accordingly. Each sub-lot will be divided into syringes (or bags) each containing a maximum of 1 mL of total packed islet cells (if syringes are used). If more than one sub-lot of the islet preparation is to be administered (i.e., where sub-lots are identified as having different islet purity), the lot with the higher purity will be administered first. Mixing sub-lots together for simultaneous administration is not permitted.

The islets will be injected slowly (each syringe over a period of at least 5 minutes) by [name] or a co-investigator. During the injection, the syringe is turned constantly to avoid sedimentation of the islets and clumping. If the bag system is used, the islets are infused by gravity.

Portal pressure will be monitored before and after infusion of one syringe load (50 mL volume containing 1 mL of tissue). Any change in portal pressure will be documented, and if the intra-portal pressure rises above 22 mmHg, infusion of subsequent syringes must be held until the pressure falls below 18 mmHg. If the bag system is used, the portal pressure is taken intermittently, and if the intra-portal pressure rises above 22 mmHg, the infusion must be held until the pressure falls below 18 mmHg. The bag

system must be repetitively and gently shaken to keep the islet preparation in suspension and avoid clumping.

Following each infusion, if the portal pressure remains elevated above 22 mmHg for longer than 10 minutes, then no further infusion will be administered through the hepatic vein, and the procedure will be terminated.

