The procedure, duration of injection, number of syringes injected and discarded, and portal pressures will be recorded in the case report form. Also, any adverse event occurring during the transplant process will be recorded in the case report form.

After successful completion of the islet infusion, the catheter and syringe or bag system will be rinsed with an additional 20 mL of transplant media, which is infused through the cannula over approximately 2 minutes, and a final portal pressure documented. Under ultrasound or fluoroscopic guidance with very minimal further contrast use, the sheath tip is withdrawn from the main portal vein into the liver parenchyma. Contrast media (iodinated contrast or if allergic, CO₂ or gadolinium) is used to confirm extraportal position of the sheath. While the subject continues to be monitored, Avitene microfibrillar collagen hemostat (BARD, Davol Inc., Warwick, RI) paste mixed with diluted contrast is injected into the sheath to seal the liver parenchymal tract. Under fluoroscopic guidance the sheath is withdrawn while injecting the Avitene paste until the sheath is removed and Avitene paste seals the liver parenchymal tract to the peripheral portal vein. Alternatively, the catheter is withdrawn slowly over 30 minutes or more, allowing formation of an autologous blood clot. The catheter is then removed completely and the subject returns to the Transplant Unit with instructions to lie recumbent for 4 hours. Abdominal ultrasound and Doppler examination of the liver are performed the day after the procedure to exclude procedure related complications such as portal vein thrombosis or intra-abdominal bleeding (see Section 6.6.6 and Appendix *Post-Transplant Orders*).

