The resulting cooled crude extract, which contains a mix of exocrine tissue and islets, is purified with density gradients in an apheresis system (model 2991, COBE Laboratories). The COBE 2991 and the gradient mixer are placed in a refrigerated room to reduce the effects of temporary warming on the cells during the separation process, which occurs under hypoxic conditions. The gradient maker is located under the hood. The cold room temperature is 1-4° C resulting in a maximal gradient temperature of 8° C during gradient centrifugation as observed during the validation process. Two layers of solution at different density are slowly added to the COBE 2991 via a two-beaker system by using a peristaltic pump. While adding the layers to the COBE, the COBE spins at 1,800-2,000 rpm. Once the gradient has been completely pumped into the sterile COBE bag, the islet suspension is added in the same manner. The UW islet suspension

mixture is centrifuged at 1,800-2000 rpm for 3-5 minutes. The COBE is then used to pump the mixture, which is separated by density, into twelve 250 mL conical tubes located in the hood and partially filled with 230 mL of wash media. Each fraction is sampled (500 µl) with the sample being viewed under a microscope to determine which fraction(s) contain the islets of greatest purity, i.e., the greatest islet to exocrine tissue ratio. Fractions of the greatest purity are combined. Fractions of fair islet yield with fair purity are also combined with one another. Fractions that have poor purity of < 10% or fewer islets are discarded. In any case, the total volume of tissue recombined will not exceed 15 mL. The purified islet cells are then re-suspended in 250 mL of cold M199 media supplemented with 4.7% human albumin wash solution, and washed three times via centrifugation at 1,100 rpm for 1 minute. Samples of cells and supernatant are taken from the final product for quality control to define whether release criteria are met as addressed below. Supernatant sampling is performed after final centrifugation by drawing 50 mL of supernatant into a 50 mL conical tube.

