7.6.3 Assay Methods

Purity

Islets will be stained with dithizone. Dithizone bonds with the zinc contained in beta and alpha cells, stains islets red, and allows investigators to differentiate islets from other tissue. Microscopy is used to gauge the ratio of islets to other tissue in a given sample within a visualized field.

Islet Yield (Islet Enumeration)

Islets will be stained with dithizone as described above. Every visualized islet identified within a sample will be recorded and sorted according to its Equivalent Islet Number (EIN). That is, based upon the observed islet diameter at a given magnification via

microscopy, islets are assigned values according to size. A larger islet, therefore, counts more than a smaller islet in terms of its islet equivalent. The Equivalent Islet Numbers are totaled and multiplied by a dilution factor (weight of the islet suspension within a conical tube). The result is the total islet yield (EIN) for the isolation.

Settled Volume Assessment

Tissue volume is evaluated by visualization of pellet immediately after centrifugation. An alternative method to assess tissue volume is by aspirating the tissue into a glass pipette and allows the tissue to settle in the pipette.

Viability

Fluorescent dyes fluorescent diacetate (FDA) and propidium iodide (PI) or sitogreen and ethidium bromide are applied to an islet sample. The sample is observed using a fluorescent microscope with appropriate filters. Viable islets will stain a bright green and dead islets will stain red. An investigator will record the ratio of viable islets to non-viable islets based upon an observation of the sample.

Tissue Transplant Volume

The final islet suspension is centrifuged within a 250 mL conical tube. The packed cell volume at the bottom of the conical tube is measured using the calibrations on the tube. This amount represents the volume of tissue to be transplanted.

Microbiological Assessment

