7.6.4 Criteria for Quality Control Testing

Islet purity, yield, tissue volume, viability, direct Gram staining, and endotoxin levels will be analyzed prospectively and will determine the decision whether a preparation can be released for transplantation. Bacterial and fungal growth, islet potency determined by glucose static incubation, and transplantation into nude mice are performed retrospectively. Acceptable parameters of quality control testing of the final product are summarized in Table 7-4.

Table 7-4 Acceptable Parameters of Quality Control Testing

QC test	Acceptable Parameters
Purity	≥ 50%
Yield	≥ 5,000 EIN/Kg
Viability	≥ 70% for high purity layer and >29% for combined preparation
Tissue Volume	≤ 15mL
Endotoxin	≤ 5 EU/Kg bodyweight of recipient
Bacteriology	Gram staining negative Aerobic growth negative Anaerobic growth negative Fungal growth negative
GSI and Bioassay	To be determined during the study, based on correlation with observed clinical outcomes

7.6.5 Action Plan in the Case of a Positive Sterility Result after Product Release

Since results of sterility testing are not available until after administration of the islets, a plan of action for patient notification and treatment in case of positive results in the sterility culture is in place. Any organism detected from the final implanted islet cell preparation will be further evaluated for species identification and antibiotic sensitivity and resistance, and the recipient of the preparation will be treated as medically indicated.

The PI will evaluate the recipient for signs and symptoms of infection. The PI will use vital signs, WBC, and blood cultures to screen for infection. If evidence of infection is found, the patient will be treated according to sensitivity of identified micro-organism(s) and monitored as required. Infection of the recipient by an islet preparation will be considered a serious adverse event, and the necessary action will be taken as described in Section 6.10.5 *Monitoring and Reporting of Adverse Events*.

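### Table 7-4 releases a final product of up to 15 mL of tissue, although Section 6.5.1 caps a transplant at 10 mL

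*Protocol*

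**What the plan says.** **Dosing limit.** Section 6.5.1 states that "packed cell volume may not exceed 10 mL per transplant". Its transplant procedure describes the preparation as having a "total packed cell volume of less than 10 mL". Lots above 5 mL are split by purity into two sub-lots during purification. When both are given, "the lot with the higher purity will be administered first". A syringe holds at most 1 mL of packed cells, and the case report form records the "number of syringes injected and discarded".

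**Release limit.** Table 7-4 (Section 7.6.4) lists the acceptable results for the final product: tissue volume no more than 15 mL and yield at least 5,000 EIN/kg. Section 7.6.4 names both among the tests that "will determine the decision whether a preparation can be released for transplantation". Table 7-3 places tissue volume only at QC2, after culture and before transplantation.

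**Sequence.** Under 6.5.1 the subject waits in the Transplant Unit until the lot is released and the cross-match is negative. "Then the subject will be brought to the radiology suite for transplantation."

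**In-process limit.** The purification step in Section 7.2.2 has its own limit: "the total volume of tissue recombined will not exceed 15 mL".

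**The concern.** Two sections of one protocol give different upper limits for the same infusion, and the looser one governs release. A lot between the limits is acceptable under Section 7 and too large under Section 6. No sentence in the text supplied says that such a lot must be reduced to 10 mL, when, or by whom.

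The second effect concerns dose. The 5,000 EIN/kg criterion is applied to the released product. If part of that product may not be given, the criterion has been met on tissue that includes an amount to be left out, so the release decision does not describe the dose the subject can receive.

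Final packed cell volume is one of the safety parameters for each islet preparation in Section 6.10.1, and Section 6.2 says the series is to support a biological license application. A release specification looser than the dosing limit should not stand in that file.

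**Working it through.** **1. Does the 15 mL limit apply at release?** Neither limit is derived by a formula, so this is a comparison of text. Table 7-4 is headed by a sentence about the final product, and tissue volume is a QC2 test that decides release. Section 7.6.3, under Tissue Transplant Volume, says of the packed cell volume of the final suspension: "This amount represents the volume of tissue to be transplanted". The pooling limit in 7.2.2 is a separate, pre-culture rule that happens to use the same number. So 15 mL is a release limit as written.

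**2. Size of the gap.** 15 − 10 = 5 mL, and 15/10 = 1.5, so the release limit is 50% above the cap.

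**3. Do such volumes arise?** Inputs are the tissue volumes in Tables 7-5 (after purification) and 7-6 (transplanted). Both tables label the unit as millimeter, read here as mL. Recomputed means (SD) agree with those printed: Table 7-5, UIC 4.75 (3.22) and CIT 5.41 (3.20); Table 7-6, UIC 4.7 (2.6) and CIT 2.9 (1.3).

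- Table 7-5: 5 of 40 lots exceed 10 mL (4 of 31 UIC, 1 of 9 CIT); none exceeds 15 mL.
- Table 7-6: 0 of 42 products exceed 10 mL; the maximum is 9.0 mL.

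The five large lots appear in both tables:

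| Lot | After purification (mL) | Transplanted (mL) | Transplanted EIN/kg |
|---|---|---|---|
| H045 | 11 | 5.0 | 9,352 |
| H085 | 14 | 9.0 | 9,937 |
| H319 | 10.6 | 4.6 | 8,412 |
| H368 | 10.7 | 1.9 | 10,363 |
| C038 | 12.7 | 3.1 | 5,176 |

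All five are listed as transplanted at 1.9 to 9.0 mL and above 5,000 EIN/kg. The tables are not a clean before-and-after series: among the 31 UIC lots, the Table 7-6 volume is larger in 14, smaller in 16 and equal in 1. Volumes at QC2 release are not tabulated, so the frequency of a 10 to 15 mL lot at release is unknown.

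**4. What trimming could do to dose.** Assume, as the worst case, that islets are spread evenly through a lot of volume V mL.

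- Fraction kept when cut to 10 mL = 10/V.
- Dose from a lot released at exactly 5,000 EIN/kg = 5,000 × 10/V.
- Yield needed at release to keep 5,000 EIN/kg = 5,000 × V/10.

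| V (mL) | Fraction kept | Dose if released at 5,000 | Yield needed |
|---|---|---|---|
| 11 | 0.909 | 4,545 | 5,500 |
| 12.5 | 0.800 | 4,000 | 6,250 |
| 14 | 0.714 | 3,571 | 7,000 |
| 15 | 0.667 | 3,333 | 7,500 |

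Lots above 5 mL are split by purity, so the tissue left out would normally be the poorer part and the loss smaller. At 15 mL the loss ranges from near 0 to 33%.

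**The case against.** The strongest reply is that little follows from the mismatch, and several parts of it stand.

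- **The cap binds.** A reader might infer that the protocol permits a 15 mL infusion. It does not: 6.5.1 forbids more than 10 mL whatever the release table says.
- **Nothing new emerges in radiology.** A reader might infer that a shortfall would come to light only once the subject has been sent for transplant. Volume and yield are both prospective release tests, so whoever releases the lot has both figures.
- **No stated minimum dose is broken.** A reader might treat an infused dose below 5,000 EIN/kg as a breach. That figure is a release criterion. Section 6.5.1 sets no minimum infused dose per transplant; its requirement is cumulative, more than 10,000 IE/kg after two transplants. It also ends an infusion if portal pressure stays above 22 mmHg for longer than 10 minutes, so a delivered dose below the released dose is already foreseen.
- **Handling is partly implied.** Giving the purer sub-lot first in 1 mL syringes, with discards recorded, lets staff stop at ten syringes and leave out poorer tissue. This helps less on the infusion-bag route, and it remains an inference.
- **Past yields do not measure the risk.** It is tempting to compare the yields needed after trimming with those in Table 7-6. Every product there was 9.0 mL or less and would not have been trimmed.
- **The measures may differ.** The cap is on packed cell volume. The Tissue Volume row of Table 7-3 (pipette or centrifuged pellet) resembles the Settled Volume Assessment in 7.6.3. The methods overlap, so this is an uncertainty, and the fix should settle it.

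The Transplant Release Form and the SOPs are not in the text supplied and may contain a reduction step. None of this makes the two written limits agree.

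**Conclusion.** The point holds as an inconsistency in a stated threshold. Table 7-4 passes lots above 10 and up to 15 mL that 6.5.1 forbids infusing whole, and it judges yield on more tissue than may be given. The release limit is the one to change, because the 10 mL cap appears twice in 6.5.1 and every tabulated transplant respects it.

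The practical impact appears small. No excess infusion is authorised, no past breach is shown (0 of 42 products above 9.0 mL), and all five lots that were large after purification were transplanted within the cap and above 5,000 EIN/kg. Table 7-6 cannot prove that no future lot would fall between the limits. Primary endpoint, sample size and analysis are unaffected.

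The conclusion rests on the protocol wording alone and on reading the two volume terms as the same quantity. The 33% upper bound on dose loss also assumes uniform islet density.

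**What to change.** In Table 7-4, set tissue volume to no more than 10 mL, measured at QC2 on the amount to be infused and by the same method as the 6.5.1 cap. Apply the 5,000 EIN/kg criterion to that same amount. Keep 15 mL only in the purification step of Section 7.2.2, labelled as a post-purification in-process limit. Add a sentence to 6.5.1: a lot above 10 mL is reduced before release, lower-purity tissue first, or rejected, and the reduced volume and yield are recorded on the release form.

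The cost is one table entry and a few words in two sections, plus an update of any SOP or release form that repeats 15 mL. Under Document Control in Section 7.5.3, an SOP change needs approval by the Director and the Quality Assurance Manager, and staff retraining. The downside is that a lot above 10 mL must be trimmed or rejected before release. This looks rare, but the tabulated data cannot exclude the loss of an occasional lot.

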6.5.2 Immunosuppression Dosing and Administration

Participants in the trial will receive immunosuppression using agents approved by the FDA for organ transplantation and evaluated for use in human islet transplantation under IND to prevent allotransplant rejection. Subjects will receive basiliximab, sirolimus, tacrolimus, and etanercept in the immunosuppressive regimens. Subjects who are sensitized to human leukocytes will receive thymoglobulin instead of basiliximab for the initial transplant. Sirolimus and tacrolimus will be given according to the Edmonton protocol as described by Shapiro et al. (14). In addition to the medications included in the Edmonton protocol, participants will receive etanercept as proposed by the University of Minneapolis group and based on experimental data indicating that TNF alpha receptor antagonist improves Islet graft function and engraftment (27). It should be noted that under this protocol, corticosteroids are omitted from the post-transplant immunosuppressive regimen. Mycophenolate mofetil may be used for subjects who do not tolerate the adverse effects of sirolimus or tacrolimus. Other immunosuppressant medications may be used for subjects who do not tolerate the adverse effects of sirolimus, tacrolimus. or mycophenolate mofetil.

Patients presenting with preformed antibodies against human leukocyte antigens will receive a more intense induction protocol with the addition of a polyclonal anti-T-cell antibody preparation (Thymoglobulin).

Beginning with the initial transplant, a steroid free immunosuppressive regimen will be administered to all subjects. Subjects will receive initial doses of basiliximab, sirolimus, low dose tacrolimus, and etanercept according to the following schedule (see Section 6.5.4).

Basiliximab (Simulect®) Regimen

Basiliximab will be administered at a dose of 20 mg iv given within two hours before transplant, and 20 mg iv at week 2 after transplant for a total of 2 doses. If a second or third transplant occurs and no basiliximab was given in the preceding seven days, then the dosing regimen will begin at the time of transplant. If basiliximab has been administered within the past seven days, then the dose at transplant is omitted, and one dose is given two weeks after the last dose of basiliximab. Basiliximab will not be administered for the initial transplant in patients who are sensitized to human leukocytes and receive thymoglobulin.

Rabbit anti-human thymocyte immunoglobulin (ATG) (Thymoglobulin®) Regimen

Thymoglobulin® will be administered to patients who are sensitized to human leukocyte antigens for the initial transplant only. The first dose will be 1 to 1.5 mg/kg IV given over 6 hours immediately pre-transplant. The second dose will be 1 to 1.5 mg/kg iv over 6 hours on day 1 after transplant. Three subsequent doses of 1 to 1.5 mg/kg iv over 6 hours will be given on days 2, 3, and 4 post-transplant.

Premedication will be as follows:

- Acetaminophen (Tylenol®) 650 mg po 1/2 hour before and midway through Thymoglobulin infusion
- Diphenhydramine (Benadryl®) 50 mg po 1/2 hour before and midway through Thymoglobulin infusion
- Methylprednisolone (Solu-Medrol®) 1 mg/kg iv one hour before and midway through the first Thymoglobulin infusion

Sirolimus (Rapamune®) Regimen

Sirolimus will be administered at a loading dose of 0.2 mg/kg per day po immediately pre-transplant, and continued at a dose of 0.1 mg/kg/day each morning. Subsequently, trough serum blood levels of sirolimus will be analyzed by HPLC (two times per week initially, until trough levels are stable and within target range), and the dose will be adjusted to the target range of 12-15 ng/mL for the three months following the most recent islet infusion. When a subsequent transplant occurs, the loading dose is not used, and the subject continues on the current dosing regimen. After three months following last transplant, the target serum level will be lowered to 7-10 ng/mL.

Mycophenolate Mofetil (CellCept®) Regimen

Mycophenolate mofetil may be used for subjects who do not tolerate the adverse effects of sirolimus or tacrolimus, and will be administered at a dose of 500 mg to 1500 mg bid po for the duration of islet graft functioning.

Tacrolimus (Prograf®) Regimen

Tacrolimus will be administered at a dose of 1 mg po given immediately before transplantation, and will be continued at a dose of 1 mg po given bid. As soon as 12-hour trough tacrolimus levels (IMx assay, Abbott Laboratories) are available, the dose will be adjusted to maintain target trough levels of 3-6 ng/mL throughout the study. When a subsequent transplant occurs, the subject continues on the current dosing regimen (14).

Other Immunosuppressant Medications

Other immunosuppressant medications may be needed for subjects who do not tolerate sirolimus, tacrolimus, or mycophenolate mofetil. If azathioprine is planned, the subject may be tested for the presence of thiopurine methyltransferase (TPMT), the main enzyme responsible for inactivating toxic products of azathioprine metabolism. Test results may help to evaluate the risk for adverse effects of azathioprine. Patients with homozygous deficiency of TPMT have low enzyme activity and are at increased risks for side effects such as pancytopenia (28, 29). Azathioprine will be administered at a dose of 100 to 150 mg daily. Patients with heterozygous deficiency have 50% of enzyme activity and have been shown to respond well and tolerate at reduced dose(30). Trough levels are not measured.

Etanercept (Enbrel®) Regimen

Etanercept will be administered at a dose of 50 mg iv before islet transplantation, and will be continued at a dose of 25 mg subcutaneously on the 3rd, 7th, and 10th post-transplantation days.

